Subjects who receive blinded therapy in Induction Period 2 during Weeks 12 to 24 will be allowed to taper their corticosteroids at the discretion of the Investigator. While stopping the taper and/or increasing the dose back to baseline level is permitted, increasing doses above the Baseline dose is prohibited.

Follow-Up Period/Premature Discontinuation (PD)

Subjects in Sub-Studies 1 & 2 may discontinue treatment at any time during the study participation (Section 5.4). Subjects who end study participation early will have a PD visit and complete the procedures outlined for the PD visit in Appendix C as soon as possible after the last dose of study drug and preferably prior to the administration of any new therapies.

Subjects who discontinue the study or subjects who complete the Week 12/Week 24 visit and do not roll-over into Study M16-066 will have a follow-up call 140 days from the last dose of study drug to obtain information on any new or ongoing AEs.

Re-Screen

Subjects in Sub-Studies 1 & 2 who initially screen fail for the study may be permitted to re-screen following re-consent. The subject must meet all the inclusion and none of the exclusion criteria at the time of re-screening in order to qualify for the study. There is no minimum period of time a subject must wait to re-screen for the study, unless a subject has a positive COVID-19 molecular (i.e., PCR) test per Exclusion Criterion 30.

If the subject had a complete initial screening evaluation including the TB test, Hepatitis B virus (HBV), Hepatitis C virus (HCV), human immunodeficiency virus (HIV) and electrocardiogram (ECG), these tests will not be required to be repeated for re-screening provided the conditions noted in Section 5.3.1.1 are met and no more than 90 days have passed.

If a subject is being rescreened within 14 days (\leq 14 days have passed) from the collection date of the previous screening laboratory testing, repeat laboratory testing for chemistry/hematology, urinalysis, serum pregnancy, and *C. difficile* are not required unless, in the opinion of the Investigator, the subject's health status has changed.

If a subject is being rescreened more than 14 days ($>$ 14 days have passed) from the collection date of the previous screening laboratory testing then chemistry/hematology, urinalysis, serum pregnancy, and *C. difficile* should be repeated during rescreening.

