6.1.3 Relationship to Study Drug

The investigator will use the following definitions to assess the relationship of the adverse event to the use of study drug:

Reasonable Possibility	After consideration of factors including timing of the event, biologic plausibility, clinical judgment, and potential alternative causes, there is sufficient evidence (information) to suggest a causal relationship.
No Reasonable Possibility	After consideration of factors including timing of the event biologic plausibility, clinical judgment and potential alternative causes, there is insufficient evidence (information) to suggest a causal relationship.

For causality assessments, events assessed as having a reasonable possibility of being related to the study drug will be considered "associated." Events assessed as having no reasonable possibility of being related to study drug will be considered "not associated." In addition, when the investigator has not reported a causality or deemed it not assessable, AbbVie will consider the event associated.

If an investigator's opinion of no reasonable possibility of being related to study drug is given, an other cause of event must be provided by the investigator for the serious adverse event.

6.1.3.1 **Lack of Efficacy or Worsening of Disease**

[figure not shown]
Events that are clearly consistent with progression of the underlying disease (UC) are considered an expected outcome for this study and will not be subject to expedited reporting.

6.1.4 **Adverse Event Collection Period**

All adverse events reported from the time of study drug administration until 140 days, from the last dose of study drug have elapsed will be collected, whether solicited or spontaneously reported by the subject. In addition, serious adverse events and protocol-related nonserious adverse events will be collected from the time the subject signed the study-specific informed consent.

Adverse event information will be collected as shown in Figure 4.

Figure 4. Adverse Event Collection

6.1.5 **Adverse Event Reporting**

In the event of a serious adverse event, whether associated with study drug or not, the Investigator will notify Clinical Pharmacovigilance within 24 hours of the site being made aware of the serious adverse event by entering the serious adverse event data into the electronic data capture (EDC) system. Serious adverse events that occur prior to the site having access to the RAVE® system, or if RAVE is not operable, should be documented

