3.2 Secondary Endpoint(s)

Secondary endpoints are:

1. The achievement of clinical response per Adapted Mayo score at Week 12
2. The achievement of endoscopic improvement at Week 12
3. The achievement of histologic endoscopic mucosal improvement (HEMI) at Week 12
4. The achievement of endoscopic remission at Week 12
5. The achievement of clinical response per Partial Adapted Mayo score at Week 4
6. The achievement of no bowel urgency at Week 12
7. The achievement of no abdominal pain at Week 12
8. The achievement of histologic endoscopic mucosal remission (HEMR) at Week 12

9. Change from Baseline to Week 12 in Functional Assessment of Chronic Illness Therapy-Fatigue (FACIT-Fatigue)
10. Change from Baseline to Week 12 in Inflammatory Bowel Disease Questionnaire (IBDQ) total score
11. Occurrence of UC-related hospitalizations through Week 12
12. The achievement of no nocturnal bowel movements at Week 12
13. The achievement of no tenesmus at Week 12
14. Change from Baseline to Week 12 in number of fecal incontinence episodes per week
15. Change from Baseline to Week 12 in number of days per week with sleep interrupted due to UC symptoms

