- Subjects will then be characterized as responders or non-responders based on MI imputed datasets. Using the CMH model adjusted by stratification factors (Advanced Therapies-IR status (yes vs no), baseline steroid use (yes vs no), and baseline Adapted Mayo score (≤ 7 vs > 7)), the imputed endpoints will be analyzed using each of the 30 datasets. SAS PROC MIANALYZE will be used to generate the final inferences of the risk difference between risankizumab treatment group and placebo group, using Rubin's rule. Note that measurements will be set to missing on or after the date of the UC-related corticosteroids intercurrent event or the occurrence of the UC-related surgery before applying MI. After the MI imputation, an NRI override will be implemented for missing values 1) due to reasons other than COVID-19 infection or logistic reasons or geo-political conflict in Ukraine or surrounding area, or 2) on or after the date of the UC-related corticosteroids intercurrent event, or 3) on or after or the date of the

UC-related surgery intercurrent event. That is, regardless of MI imputed values, subjects satisfying 1) or 2) will be considered as "non-responder" for binary efficacy endpoints.

- For binary efficacy endpoints of occurrence of hospitalization and the occurrence of UC-related surgeries, As Observed (AO) analysis will be used.
 - As Observed: The AO analysis will not impute values for missing evaluations, and thus a subject who does not have an evaluation on a scheduled visit will be excluded from the AO analysis for that visit. AO will include all values collected in the study regardless of intercurrent events.
- Tipping Point Analysis for Binary Endpoints

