For UC-related hospitalizations through Week 12, to consider Missing-Not-At-Random (MNAR) assumption due to different dropout rates between treatment groups, a supplementary analysis will be performed based on exposure adjusted occurrence of UC-related hospitalizations through Week 12. Exposure adjusted occurrence of UC-related hospitalization will be analyzed based on incidence rates. Incidence rates for hospitalization will be calculated as the number of patients with the respective event divided by the time at risk. For patients with an event during the study period, time at risk is the patient-years (PYs) from the first dose date to the first event before Week 12. For patients without an event during Period 1, time at risk is PYs from first dose date to the end of study follow-up period, where the follow-up period starts from the first dose date to the last dose date in Period 1+ 140 days if prematurely discontinues the study drug without entering Period 2 or M16-066, or the first dose date of Period 2 or M16-066 if enters Period 2 or M16-066, whichever occurs earlier. The event date is defined as the date of admission to the hospital for hospitalizations. The incidence rate difference, 95% CI and p-value are calculated to evaluate the statistical significance of the difference between risankizumab 1200 mg IV group and placebo group using normal approximation to Poisson distribution. The analysis will be based on the AO data.

The continuous secondary endpoints will be analyzed based on ITT2 by RTB-MI with MMRM (for endpoints with more than one post-baseline visits) or with ANCOVA (for endpoints with one post-baseline visit) and the corresponding analyses are specified in Section 9.2.2. The least square (LS) mean and 95% CI for each randomized treatment group and the LS mean treatment difference, the associated 95% CI and the p-value between risankizumab 1200 mg IV group and the placebo group will be provided. Considering unequal variances due to the unequal sample size in the two treatment groups (2:1 randomization), a sensitivity analysis will be performed for continuous secondary

endpoints with only a single post-baseline measure using an ANCOVA model that estimates variance by treatment group.

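### The exposure-adjusted hospitalization analysis counts events only to Week 12 but credits event-free early stoppers with 140 days beyond their last dose

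*SAP*

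**What the plan says.** Secondary endpoint 11 (SAP Section 3.2) is "Occurrence of UC-related hospitalizations through Week 12". Its main analysis is a stratified CMH test on as-observed data. SAP Section 9.4.2 adds a rate analysis because the missing data may not be missing at random: "due to different dropout rates between treatment groups, a supplementary analysis will be performed", based on "exposure adjusted occurrence of UC-related hospitalizations through Week 12".

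The rate is the number of subjects with an event divided by time at risk. Time at risk has two definitions:

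- For a subject with an event, it runs "from the first dose date to the first event before Week 12".
- For a subject without an event, it runs from first dose to the end of study follow-up. That end is set by a rule extending "to the last dose date in Period 1+ 140 days if prematurely discontinues the study drug without entering Period 2 or M16-066", or by the first dose of Period 2 or M16-066 for a subject who enters either. The earlier date applies.

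The output is a rate difference with 95% CI and p-value, from a normal approximation to the Poisson distribution, on as-observed data.

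**The concern.** Numerator and denominator cover different periods. An event counts only if it falls by Week 12, but an event-free early stopper goes on accruing time at risk well beyond it. The earlier-date clause does not help: it chooses between last dose plus 140 days and the first dose of the next stage, and neither is Week 12.

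The surplus time belongs only to subjects who stop early, so the denominator grows with dropout in a way the event count cannot match. An analysis added to deal with unequal dropout therefore brings in a dropout-dependent distortion of its own. A reader would take its rate difference, CI and p-value as evidence on whether the main result is robust to dropout.

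The rule also names no end date for a subject who completes Period 1 and does not roll over. Protocol Section 5.1 expects such subjects: "subjects who complete the Week 12/Week 24 visit and do not roll-over into Study M16-066 will have a follow-up call 140 days".

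**Working it through.** The documents give no hospitalization rate, dropout rate or patient-years for this analysis, so there is no planned figure to reproduce.

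**Inputs from the documents.** Doses at Weeks 0, 4 and 8 (days 0, 28, 56) and arms of 644 risankizumab and 322 placebo (SAP Section 2.2); 140 days after last dose (SAP Section 9.4.2). Week 12 is taken as day 84.

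**Assumed.** Early-stop fractions *d*, 12-week risks, and follow-up of everyone through Week 12.

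**Step 1: time credited to one event-free early stopper** = last dose day + 140.

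| Last dose | Days credited | Days after day 84 | Share after day 84 |
|---|---|---|---|
| Day 0 | 140 | 56 | 40% |
| Day 28 | 168 | 84 | 50% |
| Day 56 | 196 | 112 | 57% |

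The last row applies only if a subject who received all three Period 1 doses can count as having stopped study drug prematurely, which the text leaves unclear.

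**Step 2: effect on the rate ratio at equal true risk.** Ignoring the small time contributed by subjects with events, mean credited days = (1 − *d*) × 84 + *d* × (last dose day + 140). With equal events per subject, the placebo-to-risankizumab rate ratio is risankizumab mean days divided by placebo mean days.

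| *d*, placebo vs risankizumab | Last dose | Mean days, placebo | Mean days, risankizumab | Rate ratio |
|---|---|---|---|---|
| 10% vs 3% | Day 0 | 89.6 | 85.7 | 0.956 |
| 10% vs 3% | Day 28 | 92.4 | 86.5 | 0.936 |
| 10% vs 3% | Day 56 | 95.2 | 87.4 | 0.918 |
| 15% vs 5% | Day 0 | 92.4 | 86.8 | 0.939 |
| 15% vs 5% | Day 28 | 96.6 | 88.2 | 0.913 |
| 15% vs 5% | Day 56 | 100.8 | 89.6 | 0.889 |

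In patient-years, placebo through Week 12 is 322 × 84 / 365.25 = 74.1. The plan credits 322 × 89.6 / 365.25 = 79.0 (10%, one dose) to 322 × 96.6 / 365.25 = 85.2 (15%, two doses), which is 7% to 15% too much. For risankizumab the corresponding figures are 644 × 84 / 365.25 = 148.1 against 151.1 (3%, one dose) to 155.5 (5%, two doses), or 2% to 5% too much.

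**Step 3: the same check with event subjects' time included.** Take a constant hazard λ = −ln(1 − *r*)/84 for 12-week risk *r*. The expected rate is *r* / [*r*/λ − 84(1 − *r*) + (1 − *r*) × mean event-free days]. Early stops are spread evenly over doses 1–2 or doses 1–3.

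- At equal *r* of 1%, 3% or 5%, early stopping of 15% placebo vs 5% risankizumab gives a risankizumab-to-placebo ratio of 1.08 to 1.10 (the inverse of Step 2's ratio) instead of 1.00.
- With 5% placebo vs 15% risankizumab it is 0.91 to 0.93. With 5% in each arm it is 1.00, but both rates are 4% to 5% too low.
- With everyone capped at day 84, both arms give 4.37, 13.24 or 22.30 per 100 patient-years at risks of 1%, 3% or 5%. The ratio is 1.00 whatever the early-stop fractions.

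**Step 4: effect on the test when a true difference exists.** z = rate difference / √(sum over arms of events / patient-years²), with early stopping of 20% placebo vs 5% risankizumab.

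| True risk, placebo vs risankizumab | Difference per 100 PY, capped (z) | Difference per 100 PY, as written (z) |
|---|---|---|
| 5% vs 1% | −17.9 (−3.08) | −14.5 to −15.0 (−2.94 to −2.96) |
| 3% vs 1% | −8.9 (−1.93) | −6.9 to −7.2 (−1.76 to −1.79) |

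**The case against.** **The windows might be meant to match.** The paragraph is loosely worded: one clause refers to events in the study period and another to events in Period 1. The Period 1 adverse-event window in SAP Section 10.2.1 also runs to 140 days after last dose for subjects who do not continue, and Protocol Section 6.1.4 says adverse events "until 140 days, from the last dose of study drug have elapsed will be collected". If hospitalizations were counted over that whole window, numerator and denominator would agree. That reading conflicts with the through-Week-12 label, with endpoint 11 and its estimand, and with the clause ending event time before Week 12. It would also leave an early stopper first hospitalized after Week 12 with no defined time at risk. The text needs correcting on either reading.

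**The stakes are limited.** This stands. The analysis is supplementary, no decision rule uses its p-value, and in neither Step 4 scenario does z cross 1.96. If placebo has more early stopping, the distortion works against risankizumab.

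**Events after stopping drug already count.** Up to Week 12 they do: "AO will include all values collected in the study regardless of intercurrent events". The fault lies in the credited time after Week 12, when no event can count.

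**The gap for completers is narrower than it looks.** SAP Section 2.2 groups subjects who are eligible for Period 2 but do not receive it with early terminations, so they may be meant to fall under the 140-day rule. That passage concerns leaving the study, not stopping study drug. The clear gap is Period 1 responders who do not enter M16-066; their number is unknown.

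**Day 84 is an assumption.** The SAP sets no day for this cut-off, and visits have a ±7-day window (Protocol Appendix C, footnote a). The cap should therefore use whatever Week 12 cut-off the main analysis uses.

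**Conclusion.** The concern holds. As written, the analysis pairs a Week 12 event count with a denominator that extends past Week 12 only for early stoppers. Under assumed early stopping of 10% vs 3% or 15% vs 5%, it shifts a null rate ratio by about 4% to 9% when the last dose is on day 0 or 28, and by up to 11% when it is on day 56. The direction depends on which arm stops more, and equal stopping leaves the ratio undistorted.

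The mismatch and the credited days follow from the text; the size rests on dropout rates that the documents do not supply. The CMH analysis of endpoint 11 and the multiplicity procedure are untouched. The rule should still be corrected, because the distortion arises from the very imbalance this analysis is meant to address.

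**What to change.** Replace the rule for event-free subjects in SAP Section 9.4.2. Time at risk should run from first dose to the earliest of:

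- the Week 12 cut-off used in the main as-observed analysis (nominally day 84);
- the first dose of Period 2;
- the first dose in M16-066;
- the actual end of hospitalization or adverse-event follow-up, meaning loss to follow-up, withdrawal of consent or death.

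Stopping study drug or leaving the study should not by itself end time at risk. Count first events over exactly this interval, and remove the looser references to the study period and Period 1. Hospitalizations after stopping drug but by Week 12 still count, and completers who do not roll over gain an end date.

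Counting events over the full 140-day follow-up would also align the windows, but the analysis would then need a new name because it would no longer describe endpoint 11.

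The cost is one SAP sentence and the matching program change. It uses dose, event and follow-up dates and needs no new assessment.

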9.5 Additional Efficacy Endpoints and Analyses

9.5.1 Additional Analyses

All additional binary efficacy endpoints specified in Section 3.3 will be analyzed based on ITT2 using the same approach as the primary approach for primary endpoint as specified in Section 9.3.2. Specifically, CMH adjusting for stratification factors will be used to construct the treatment difference, the associated 95% CI and p-value between risankizumab 1200 mg IV group and placebo group. The NRI-MI will be the primary approach for missing data handling in the analyses of binary secondary efficacy endpoints except for the occurrence of UC-related hospitalization.

All additional continuous endpoints will be analyzed based on ITT2 by RTB-MI and the corresponding analyses are specified in Section 9.2.2. The least square (LS) mean and 95% CI for each randomized treatment group and the LS mean treatment difference, the associated 95% CI and the p-value between risankizumab 1200 mg IV group and the placebo group will be provided. For time to clinical response per Partial Adapted Mayo score in Period 1, the distribution of time to clinical response including median will be estimated for each treatment group using Kaplan-Meier method and compared between the two treatment groups using stratified Log-rank test. The hazard ratio and corresponding 95% CI between the two treatment groups will also be obtained using the Cox Proportional Hazard Model. Subjects who have experienced IE2 or IE3 prior to experiencing the event (clinical response per Partial Adapted Mayo) are censored at the time of the earliest intercurrent event of IE2 or IE3. Subjects who are not experiencing the event (clinical response per Partial Adapted Mayo) are censored at the date of study discontinuation (if discontinued in Period 1) or last non-missing measurement of partial adapted Mayo score in Period 1 (if not discontinued in Period 1).

9.5.2 Induction Period 2 Efficacy Analysis

For all endpoints specified in Section 3.3, descriptive summary including point estimate (% or mean) and 95% CI will be provided for ITT2_P2 population by treatment sequence. The NRI-MI and RTB-MI will be used in the analyses of binary and continuous efficacy endpoints, respectively, as specified in Section 9.3.2. For time to clinical response per Partial Adapted Mayo score in Period 2, the distribution of time to clinical response including median time with will be descriptively summarized for each treatment group using Kaplan-Meier method.

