Subjects taking oral corticosteroids at Baseline must continue their concomitant treatment at the Baseline dose for the duration of Induction Period 1. Initiation and/or increasing doses of systemic and/or UC-related corticosteroids after Baseline is prohibited. Decreasing doses of oral corticosteroids is prohibited during Induction Period 1, except in the event of moderate-to-severe treatment related toxicities in the opinion of the investigator.

Methodology (Continued):

Subjects who enter Induction Period 2 will be allowed to taper their oral corticosteroids at the discretion of the Investigator. While stopping the taper is permitted, increasing doses above the Baseline dose is prohibited.

Dose Selection:

Sub-Study 2 (Phase 3 induction study) will evaluate IV risankizumab 1200 mg during induction. The selection of doses was informed by the analysis of safety and efficacy data, as well as the dose-response and exposure-response relationships of efficacy from Sub-Study 1 (Phase 2b dose finding study).

Induction Period 2 will evaluate IV (1800 mg [Sub-Study 1] or 1200 mg [Sub-Study 2] Q4W) or SC (180 mg or 360 mg Q8W; maintenance dosing regimen) risankizumab. The purpose of Induction Period 2 is to evaluate the efficacy and safety of re-induction of risankizumab versus starting maintenance regimen on clinical response status. Data from the Phase 2 study in subjects with CD suggested that re-induction with 600 mg IV increased both clinical response and clinical remission in subjects with inadequate response at Week 12. The selection of the SC doses is based on safety and efficacy data, as well as the exposure-response relationship, of the maintenance period during the Phase 2 study in subjects with CD that evaluated 180 mg SC risankizumab for maintenance. A higher dose of 360 mg Q8W is proposed to provide exposures reasonably separated with 180 mg Q8w dose to characterize the exposure-response relationship during maintenance phase with a potential of 360 mg Q8w dose to maintain higher response compared to 180 mg Q8w dose.

Data Monitoring Committee (DMC):

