Sub-Study 2:

Sub-Study 2 (Phase 3 induction study) will evaluate IV risankizumab 1200 mg during induction. The selection of this dose was informed by the analysis of safety and efficacy

data, as well as the exposure-response relationship of efficacy from Sub-Study 1 (Phase 2b dose finding study) where risankizumab doses of 1800 mg IV, 1200 mg IV, and 600 mg IV were evaluated. All three risankizumab doses achieved higher clinical remission rates per Adapted Mayo Score (primary endpoint) at Week 12 compared to placebo; both the 1200 mg and 1800 mg groups achieved nominal *P*-values < 0.1 (two-sided) based on pairwise comparisons. All three risankizumab dose groups also achieved higher response rates compared to placebo for other selected endoscopic, clinical and composite endpoints. Exposure-response analyses predicted greater efficacy for key endpoints (clinical remission, clinical response, and endoscopic remission) with higher risankizumab exposures and both doses of 1200 mg and 1800 mg are expected to provide better efficacy than 600 mg for subjects with UC during the induction period. While incremental efficacy is predicted with doses increasing from 1200 mg to 1800 mg, the magnitude of the difference is modest and 1800 mg is not expected to provide clinically meaningful benefit beyond 1200 mg for induction. No new safety risks were identified and the overall safety findings were consistent with the known safety profile of risankizumab.

Induction Period 2:

Induction Period 2 will evaluate IV (1800 mg [Sub-Study 1] or 1200 mg [Sub-Study 2] Q4W) or SC (180 mg or 360 mg Q8W; maintenance dosing regimen) risankizumab. The purpose of Induction Period 2 is to evaluate the efficacy and safety of re-induction of risankizumab versus starting maintenance regimen on clinical response status. Data from the Phase 2 study in subjects with CD suggested that re-induction with 600 mg IV increased both clinical response and clinical remission in subjects with inadequate response at Week 12. The selection of the SC doses is informed by the analysis of the safety and efficacy data, as well as the exposure-response relationship of efficacy, of the maintenance period during the Phase 2 study in subjects with CD that evaluated 180 mg SC risankizumab for maintenance. A higher dose of 360 mg Q8W is proposed to provide exposures reasonably separated with 180 mg Q8w dose to characterize the exposure-

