Endoscopy and efficacy evaluation will occur at Week 12. Subjects in Sub-Study 2 who achieve clinical response per Adapted Mayo score (locally read Mayo endoscopic sub score) after completion of the 12-week Induction Period 1 will be enrolled into maintenance Study M16-066. Subjects who do not achieve clinical response at Week 12, may be eligible to enter a blinded risankizumab treatment in Induction Period 2 as specified below.

Subjects are not eligible to enter Induction Period 2 until the Week 12 endoscopy has been completed, except in case of COVID-19 pandemic restrictions or geo-political conflict in Ukraine and surrounding impacted regions:

If endoscopy cannot be performed at Week 12 due to COVID-19 pandemic restrictions or geo-political conflict in Ukraine and surrounding impacted regions, clinical response will be calculated using the Partial Adapted Mayo score.

Subjects with missing endoscopy due to COVID-19 pandemic restrictions or geo-political conflict in Ukraine and surrounding impacted regions and achieve clinical response per

Partial Adapted Mayo score at Week 12 may be eligible to enroll in Study M16-066 Sub-Study 3, which is an open-label long term extension study to evaluate long-term safety of risankizumab. Subjects who do not achieve clinical response at Week 12, may be eligible to enter a blinded risankizumab treatment in Induction Period 2 as specified below.

Sub-Study 2 Induction Period 2:

At Week 12, subjects who do not achieve clinical response will be randomized by Interactive Response Technologies (IRT) to Induction Period 2, a double-blind, double dummy 12-week treatment period to evaluate reinduction with risankizumab versus starting maintenance dosing on clinical response status.

[figure not shown]
Subjects who received IV risankizumab will be randomized 1:1:1 to:

- Group 1: Risankizumab 1200 mg IV Weeks 12, 16, and 20
- Group 2: Risankizumab 360 mg SC Weeks 12, and 20
- Group 3: Risankizumab 180 mg SC Weeks 12, and 20

Subjects who received placebo induction treatment will receive:

- Group 4: Risankizumab 1200 mg IV Weeks 12, 16, and 20

The schematic of the Induction Period 2 is shown in [Figure 2](#).

Figure 2. Study Schematic of Induction Period 2

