2.3 Treatment Assignment and Blinding

In Induction Period 1, approximately 966 subjects will be randomized in a 2:1 ratio to risankizumab 1200 mg IV dose or placebo. The randomization at baseline will be stratified by number of prior failed biologics (0, 1 vs > 1), baseline steroid use (yes vs no), and baseline Adapted Mayo score (≤ 7 vs > 7).

In Induction Period 2, subjects who do not achieve clinical response and received IV risankizumab in Induction Period 1 will be randomized 1:1:1 to risankizumab 1200 mg IV, 360 mg SC and 180 mg SC groups. The randomization will be stratified by number of prior failed biologics (0, 1 vs > 1), baseline steroid use (yes vs no), and baseline Adapted Mayo score (≤ 7 vs > 7). Subjects who do not achieve clinical response and received placebo in Induction Period 1 will receive risankizumab 1200 mg IV.

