12.0 Overall Type-I Error Control

Sub-Study 1 (Phase 2b) – Induction Period 1:

Sub-Study 1 is the Phase 2b randomized, placebo-controlled dose ranging study. The primary, the ranked secondary and non-ranked secondary efficacy variables will be analyzed by treatment group for the Intent-to-Treat (ITT) analysis set for Sub-Study 1, defined in Section 4.0, at the nominal α level of 0.05 (one-sided). No multiplicity adjustment will be performed for the Phase 2b dose ranging study.

No multiplicity adjustment will be applied to non-ranked secondary efficacy endpoints listed in Section 3.2. The analysis for non-ranked secondary efficacy endpoints will be performed at the nominal α level of 0.05 (two-sided).

Sub-Study 1 – Induction Period 2:

For Induction Period 2, no multiplicity adjustment will be performed for all efficacy endpoints listed in Section 3.3. The analysis for all efficacy endpoints will be performed at the nominal α level of 0.05 (two-sided) for exploratory purpose.

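### Sub-Study 2 re-randomises Week 12 non-responders to compare re-induction with starting maintenance dosing, but the SAP never estimates that randomised difference

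*SAP*

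**What the plan says.** Purpose. Protocol section 5.6.4 states: "The purpose of Induction Period 2 is to evaluate the efficacy and safety of re-induction of risankizumab versus starting maintenance regimen". The synopsis (Dose Selection) says the same, and section 2.2 of the Sub-Study 2 SAP describes a double-blind, double-dummy period "to evaluate reinduction with risankizumab versus starting maintenance dosing on clinical response status".

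Design. In SAP 2.2, "Subjects who received IV risankizumab will be randomized 1:1:1 to" 1200 mg IV, 360 mg SC or 180 mg SC. The other non-responders are not randomised: "Subjects who received placebo induction treatment will receive" 1200 mg IV. SAP 2.3 adds, for the re-randomised subjects, "The randomization will be stratified by number of prior failed biologics", baseline steroid use and baseline Adapted Mayo score.

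Analysis. For the endpoints in SAP 3.3, section 9.5.2 says a "descriptive summary including point estimate (% or mean) and 95% CI will be provided for ITT2_P2 population by treatment sequence". Time to clinical response in Period 2 gets a Kaplan-Meier summary per group. Protocol 8.1.6.2 likewise calls for a descriptive summary of the Period 2 sets for exploratory purposes, so the two documents agree.

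**The concern.** The stated Period 2 question is a contrast between arms, and the second randomisation is what would make that contrast unconfounded. The planned tables give each arm alone. A reader who wants the answer must subtract percentages without an interval, or judge by whether the per-arm intervals overlap, which is a much stricter criterion than a 95% CI for the difference.

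Timing also matters. Under SAP 9.1, analysis and unblinding follow completion of Week 24 and database lock. A contrast written in before that point is pre-specified; one added later is post hoc.

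**Working it through.** **Step 1. Does any other text supply the contrast?**

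- SAP 9.1 makes a CMH common risk difference the default for categorical variables unless something else is specified. Section 9.5.2 specifies something else.
- The pointer in 9.5.2 to section 9.3.2 attaches to NRI-MI and RTB-MI, that is, to missing-data handling.
- SAP 9.5.1 gives differences for the additional endpoints, but as risankizumab 1200 mg IV against placebo in ITT2.
- The adverse-event differences in SAP 10.2.2 are also risankizumab against placebo.
- The Period 2 time-to-event summary has no log-rank test or hazard ratio.

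No IV-versus-SC difference is planned anywhere.

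**Step 2. The plan's own figure.** The documents give no precision or power for Period 2. The only power figure for Sub-Study 2 (SAP 2.4) is at least 90% for the Week 12 primary endpoint: 16% against 6%, 644:322, two-sided 0.05. Recomputed, it is 99.8% by the normal approximation and by simulating the Miettinen-Nurminen score test, so the stated lower bound holds. It says nothing about Period 2 except that 644 subjects start on risankizumab.

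**Step 3. Subjects per re-randomised arm (assumptions).** Suppose 35% to 45% of the 644 are Week 12 non-responders and 95% of them enter Period 2:

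- Low: 644 × 0.35 × 0.95 / 3 = 71
- High: 644 × 0.45 × 0.95 / 3 = 92

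**Step 4. Interval widths at 50% response (assumption).**

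| Quantity | Formula | n = 71 | n = 92 |
|---|---|---|---|
| Per-arm 95% half-width | 1.96 × √(0.25/n) | 11.6 points | 10.2 points |
| 95% half-width of a difference | 1.96 × √(0.5/n) | 16.4 points | 14.5 points |
| Observed gap for non-overlap | 2 × per-arm half-width | 23.2 points | 20.5 points |

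The ratio of the last two rows is 2/√2 = 1.41 whatever the assumptions, given equal arms and similar rates. Two 95% intervals that just touch correspond to z = 1.96 × √2 = 2.77, a two-sided p of about 0.006.

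**Step 5. Wider assumptions.** With 30% to 60% non-responders, 80% to 100% entry and 30% to 50% response, n per arm is about 52 to 129. The half-width of a difference is then about 11 to 19 points, and that of a single arm about 8 to 14.

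**Step 6. What this means for true differences.** With SE = √(0.5/n), which is 8.4 points at n = 71 and 7.4 at n = 92:

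- For a true 15-point difference, the CI for the difference excludes zero with probability Φ(15/SE − 1.96), about 43% to 53%.
- For a true 22-point difference, the per-arm intervals fail to overlap with probability Φ(22/SE − 2.77), about 44% to 58%.

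The thresholds in Step 4 are therefore statements about observed gaps only.

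**Step 7. Stratum sizes.** Crossing the prior-failed-biologics factor with two binary factors gives 8 strata if it has two levels and 12 if it has three. The mean per arm per stratum is 71/8 to 92/8 = 9 to 11.5, or 71/12 to 92/12 = 6 to 8. Sparse cells are likely.

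**The case against.** The strongest reply is that the protocol asks for exactly this output. Period 2 is labelled exploratory in protocol 8.1.1.1, 8.1.6 and 8.1.6.2. The Sub-Study 2 objective, hypotheses, estimands and sample size contain no Period 2 contrast. SAP 9.5.2 even adds confidence intervals to the summary that the protocol requires. The arms are independent, so a reader can form an approximate unstratified difference from the tables. SAP 3.3 lists 27 Period 2 entries, so two contrasts on each would print 54 uncontrolled intervals.

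Much of this stands: there is no conflict between protocol and SAP, and the contrasts should be limited to a few endpoints. But exploratory status removes the need for alpha, not the need to estimate the question posed. The SAP already treats subgroups this way in 9.6, with a difference, a 95% CI and no p-value. A reader's own subtraction is neither stratified nor pre-specified.

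Four stronger readings are tempting but unsupported:

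- *The Sub-Study 1 SAP estimates this contrast.* Its section 12.0 says the Period 2 analysis is "performed at the nominal α level of 0.05 (two-sided) for exploratory purpose", but names no IV-versus-SC comparison. The only pairwise comparison in its section 8.5 is against placebo.
- *Nothing marks the non-randomised group.* Section 4.0 of the Sub-Study 2 SAP labels it placebo/risankizumab, and 2.2 and 2.3 make clear who is randomised.
- *True differences of 15 to 22 points would look inconclusive.* Step 6 shows that this confuses true with observed differences. A true 15-point difference would often look inconclusive after the fix as well.
- *The second randomisation and third endoscopy are wasted.* The Week 24 endoscopy also decides entry to Study M16-066, and Period 2 gives placebo non-responders active drug.

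**Conclusion.** The gap is real and limited. Both documents give Period 2 a comparative purpose and a stratified re-randomisation to serve it, and the SAP plans no estimate of the resulting difference. The primary analysis, the ranked secondary endpoints and type I error control are unaffected. Under the assumptions of 71 to 92 per arm and 50% response, observed gaps from roughly 15 to 16 points up to 20 to 23 points would have a 95% CI for the difference excluding zero while the per-arm intervals still overlap. The absolute figures depend on assumed numbers; the 1.41 ratio between the two criteria does not, for equal arms with similar rates. This should be corrected before unblinding, as an exploratory addition.

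**What to change.** Add to SAP 9.5.2, restricted to subjects re-randomised after IV risankizumab:

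- For the main Week 24 binary endpoints (for example clinical response, clinical remission and endoscopic improvement), the risk difference with nominal 95% CI for 1200 mg IV against 360 mg SC and for 1200 mg IV against 180 mg SC.
- The CMH risk-difference method of 9.1, stratified by the Period 2 randomisation factors in 2.3. The factors in 9.1 are not the same, because 9.1 uses Advanced Therapy-IR status in place of number of prior failed biologics. State in advance a rule for collapsing sparse strata.
- For the continuous endpoints, the LS mean difference with 95% CI from the models in 9.2.2.
- A statement that these are exploratory, with no p-value and no alpha, and that the placebo/risankizumab sequence stays descriptive and outside the contrasts.

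The cost is a few lines of SAP text and some table rows from existing programs. No treatment, visit, endpoint or part of the multiplicity graph changes. The downside is wide intervals and several uncontrolled nominal CIs, which is why the endpoint list should be short.
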